Common acute side effects of psilocybin are almost all psychological, and include anxiety, changes in thought (experiencing thinking speeding up or slowing down), changes in motion perception, changes in time perception (time slowing down or speeding up), depersonalization (feeling as if one is "outside oneself"), derealization (feeling as if the world is unreal or as if one is "in a dream"), dizziness, fatigue, impaired concentration, inattention, mood lability (rapid and sometimes profound changes in mood), nausea, nervousness, parasthesias (strange bodily sensations or feelings), perceptual alterations (general), altered time perception, alteration in visual perception (distortions, illusions and imagery seen with eyes open or closed), and unusual thought or feelings about the self or the world. 25,41,46 Most of these effects are acute and last no longer than six hours. For the most part, people receiving psilocybin were able to interact, and maintained insight concerning the nature and source of their experience. However, some participants occasionally exhibited paranoid ideation or temporarily lost insight into the experimental situation. 41,46

Page 8 Version 1.16, July 18, 2022

Psilocybin produces mild sympathetic system activation. Physiological effects include pupillary dilation and detectable but moderate increases in blood pressure or heart rate . ⁴⁶ Researchers sometimes detected changes in blood pressure and heart rate only at one point in time, as sixty minutes after drug administration. ²⁵ These effects are transient and are generally gone approximately six hours after drug administration. People in previous human studies have tolerated doses of psilocybin equal to or greater than the doses employed in this study. Researchers studying the effects of 30 mg psilocybin took precautions similar to the ones we will use in this study and no reactions requiring pharmacological intervention occurred.²⁷

1.3.3.1.c. Acute side effects

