1.3.3.2. Potential risks of Niacin (active-placebo-control agent)

A participant's symptoms of depression or burnout could change or perhaps worsen during the course of the study, as symptoms might change if that individual were not participating in the study. However, there is no reason to believe that niacin &an active-placebo-control would exacerbate symptoms of depression or burnout. Niacin has expected physiological side effects that make it well suited to be used as an active placebo, including flushing, tingling, itching, and redness of the face, arms, and chest, as well as headaches, and these are documented to be transient. Other minor, transient, and occasional side effects include upset stomach, intestinal gas, and dizziness. Participants will be informed about these potential side effects, and they will be monitored throughout the drug administration visits.

1.3.3.3. Potential risks of changes or delay in participant treatments being received prior to screening

Participants will be asked to refrain from starting new medications, including OTC supplements, during the procedures involved in this study. Should circumstances warrant a change in treatment, then participants will be asked to immediately notify the study team. If medically warranted, the participant begins to experience a decline, or their provider believes a treatment change is necessary, then the participant will be withdrawn from the study and encouraged to seek treatment.

For participants who are tapering and discontinuing antidepressant medications prior to entering the study, the following safety measures will be taken:

- Participants will be required to discuss changes in their antidepressant medication with their own prescribing provider, and to provide the study staff with a written note from the provider describing the plan.
- Study staff will be in contact with a participant who is tapering their antidepressant medication weekly with a phone safety assessment that will involve use of the C-SSRS. (These safety assessments are not designated as a 'study visit' so do not appear in the study visit flowsheets in Section 3.1 that summarize research procedures).
- Participants will be required to provide the name of at least one adult who will be in continuous contact with them during the taper and discontinuation period.

1.3.3.4. Risk of Emotional Responses, Discomforts During Administration & follow-up meetings.

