1.3.3.8. Minimizing participant risks

The anticipated risks and risk mitigation strategies that will be used are summarized in the Table below.

Anticipated risk	Risk mitigation strategies	Occurrence of risk in recent published studies since 2000
Changes to any treatments a participant is receiving prior to study screening and enrollment	 Clear communication with potential participants about existing treatments (for example need to taper SSRI before study entry). Coordination between PI and participants mental health provider. 	Published studies do not report numbers of participants who had complications related to changing treatments prior to screening.
Worsening of participant mental health symptoms during the study	 Weekly phone calls from study staff to check in re participant well-being are part of the study procedures. Mental health symptoms will be assessed by study therapists during all preparation and integration psychotherapy sessions, and therapists will discuss with participants and the study team (at a weekly meeting or urgently with the PI) any issues that may warrant a change in study procedures. 	This risk has not been reported in published studies since 2000.
Increase in participant suicidality during the study	 All participants will be screened with the Columbia Suicidality Screening instrument at preparation, medication days, integration sessions, and at follow up measurements. If an increase in suicidality is measured, study staff will notify the PI immediately and arrangements for appropriate evaluation will be made with the attending psychiatrist on call at Harborview Medical Center. 	This risk has not been reported in published studies.
Intense psychological reactions during the medication session	 All study therapists will have training specifically for this issue. the therapist manual lays out first-line and second-line interventions (which are non-pharmacologic), as well as indications about when to notify the PI [name]. These interventions are based on consultation and experience at other academic centers where research with synthesized psilocybin has been conducted (NYU, Yale, Johns Hopkins). 	This risk has been reported in up to 40% of participants. In all instances, these reactions have been managed with non-pharmacologic interventions, and

Page 12 Version 1.16, July 18, 2022

		the reactions have been transient.

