Following the investigator brochure, although there have been no reports of their use in well-reported clinical trials with oral psilocybin, medications will be available for the treatment of causal symptomatic hypertension, agitation, or severe psychosis. Typically, these supplies are two dosage unitsof labetalol, nitroglycerin, lorazepam and/or diazepam, and risperidone or similar orally- disintegrating antipsychotic.

If any participant presents with an adverse reaction to the psychopharmacological agent as reported by them or assessed by a member of the research team, we will discontinue the study and call for medical assistance. Finally, the participant may be withdrawn from the study if his/her withdrawal is in the best interests of either the participant or of the research (e.g., due to a medical condition making the procedures unsafe or any condition making interpretation of the results difficult).

Niacin: (active-placebo-control agent): There is no reason to believe that niacin would exacerbate symptoms of depression or burnout or PTSD. Participants will be informed about Niacin's potential side effects, and they will be monitored throughout the drug administration visits. The rationale for using an active-placebo-control agent rather than active low dose of psilocybin (ranging 2mg -4mg), which have been used in the recent palliative care studies is because a partial response has been reported even with these low doses.

Page 14 Version 1.16, July 18, 2022

Changes or delays in treatments being received prior to screening: Participants will be asked to refrain from starting new medications to allow the participant and this study to safely proceed. If medically warranted, or the participant begins to experience a decline, or their provider believes a treatment change is necessary, then the participant will be withdrawn from the study and encouraged to seek treatment.

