2.3.2. Secondary Endpoints

- Assess symptoms of depression using the Montgomery-Asberg Depression Rating Scale (MADRS) prior to the primary endpoint at 1 week post psilocybin-assisted psychotherapy vs control psychotherapy.
- Assess symptoms of depression using the MADRS after psilocybin administration (for patients randomized to psilocybin or who receive open-label psilocybin) at 1 week, 4 weeks, 8 weeks, 12 weeks, and 6 months.
- Assess symptoms of burnout using the Stanford Fulfillment Index (SFI) at 4
 weeks post medication administration. We expect at least 50% of participants
 treated with psilocybin to show a reduction in the SFI work exhaustion and
 interpersonal disengagement subscales by at least 25% (from "a lot" to
 "moderately").
- Assess symptoms of burnout after psilocybin administration (for patients randomized to psilocybin or who receive open-label psilocybin) at 1 week, 4 weeks, 8 weeks, 12 weeks, and 6 months.
- Another secondary endpoint will assess symptoms of post-traumatic stress using the PCL5, measured at 1 week and 4 weeks after the medication session.
 We expect at least 50% of participants treated with psilocybin to show a reduction in PCL5 scores by at least 10 points (the clinically meaningful threshold for improvement).
- Assess symptoms of post-traumatic stress using the PCL5 after psilocybin administration (for patients randomized to psilocybin or who receive openlabel psilocybin) at 1 week, 4 weeks, 8 weeks, 12 weeks, and 6 months.
- A 10% or less difference in the rate of adverse events between the treatment and control arms at all study visits.

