If participants experience or report on any adverse effects or if the research staff feels that at the end of testing, that the participant has any adverse effects, participants will be able to remain until effects wear off (likely only for a short period) and medical assistance will be offered. Participants will be free to withdraw from the study whenever they wish. In addition, if any participant presents with an adverse reaction to the psychopharmacological agent as reported by them or assessed by a member of the research team, we will discontinue the study and call for medical assistance

6.5. Safety Plan for Suicidality:

During all study visits a study investigator with clinical training will assess the participant's well-being – responses, intent, plan, etc. while administering the C-SSRS (Columbia Suicidality Severity Response Scale). If these procedures result in any serious concerns on the part of the investigator, they will either ask the participant to meet with or call the PI or escort the participant to the

Page 31 Version 1.16, July 18, 2022

emergency room. If necessary, they will also call the participant's treating clinician and/or their emergency contact. As part of the consent, participants are required to designate an emergency contact person and provide their treating clinician's contact information. We will ask the treating clinician for their local plan for such emergencies so the study team can follow this plan should an emergency situation arise.

7. Payments for Participation (Economic Considerations)

Participants will not be paid for their participation. Expenses of participating in the study, such as parking will be covered by the study.

8. Assessment of Safety

- 8.1. Specification of Safety Parameters
- 8.1.1. Definition of Adverse Events (AE)

Adverse events (AEs) are defined any untoward, physical, social, economic, or psychological occurrence affecting human subjects in research. An AE can be any unfavorable or unintended event including abnormal laboratory finding, symptom, reaction, or disease. An AE does not necessarily have a causal relationship with the research, or any risk associated with the research, the research intervention, or the assessment. Adverse events involve subjects only.

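### The 10%-or-less adverse-event endpoint pools all event types against an active placebo with expected side effects, so it can be met at the dosing visit despite a large psilocybin-specific excess.

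*Combined protocol and SAP*

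**What the plan says.** Section 2.3.2 sets the endpoint as "A 10% or less difference in the rate of adverse events between the treatment and control arms at all study visits". It does not define the rate (participants with at least one event, or number of events), does not say whether 10% is absolute or relative, and does not separate events by type, grade, seriousness or relatedness.

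The definition in Section 8.1.1 is broad: "An AE can be any unfavorable or unintended event including abnormal laboratory finding, symptom, reaction, or disease". Causality is not required: "An AE does not necessarily have a causal relationship with the research". Expected drug effects are therefore not excluded.

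On the comparator, Section 1.3.3.2 says: "Niacin has expected physiological side effects that make it well suited to be used as an active placebo". It names flushing, tingling, itching, redness and headache, with occasional stomach upset, gas and dizziness. It gives no rates and describes the main effects as short-lived ("as well as headaches, and these are documented to be transient").

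On psilocybin, Section 1.3.3.1.b says: "Common acute side effects of psilocybin are almost all psychological". For intense psychological reactions in the medication session, the table in Section 1.3.3.8 says: "This risk has been reported in up to 40% of participants". Section 1.3.3.1.a also lists raised blood pressure and heart rate, nausea and headache as common physical events.

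Section 9.2 gives no analysis for this endpoint and does not include it in the testing hierarchy.

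**The concern.** The two arms are expected to produce different kinds of event. A single pooled rate treats a flush and a panic reaction as interchangeable, so events on niacin are subtracted from events on psilocybin. The control rate then reflects niacin's pharmacology as well as background risk. The trial could report that the arms differed by 10% or less in adverse events while psychological reactions occurred almost entirely on psilocybin. A larger sample or a confidence interval around the pooled difference would not cure this, because the quantity being estimated is the problem.

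**Working it through.** The plan gives no event rate, sample size or power for this endpoint, so there is no figure of its own to reproduce.

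**Inputs from the documents.** 15 participants per arm (Sections 3.1.4 and 6.1); a 10% threshold (Section 2.3.2); intense psychological reactions in up to 40% (Section 1.3.3.8), used here as 40%.

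**Assumptions.** Rate means the proportion of participants with at least one event. 10% means 10 percentage points, taken as an absolute difference. There are no background events, and one visit is considered. Niacin rates from 0% to 80% are assumed.

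**Step 1: the rule in counts.** One participant is 1/15 = 6.7 points and two are 2/15 = 13.3 points. The rule is met when the counts differ by at most one participant.

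**Step 2: chance of meeting it.** With X ~ Bin(15, p_psilocybin) and Y ~ Bin(15, p_niacin), independent,

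P(met) = sum of P(X = i) × P(Y = j) over all i, j with |i − j| ≤ 1.

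For p_psilocybin = 0.40 and p_niacin = 0, this is P(X ≤ 1) = 0.6^15 + 15 × 0.4 × 0.6^14 = 0.0005 + 0.0047 = 0.005. The second column of probabilities counts only a psilocybin excess as failure (i − j ≤ 1).

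| Niacin rate (assumed) | P(met), absolute difference | P(met), psilocybin excess only |
|---|---|---|
| 0% | 0.005 | 0.005 |
| 20% | 0.23 | 0.27 |
| 40% | 0.42 | 0.71 |
| 60% | 0.24 | 0.95 |
| 80% | 0.035 | 0.998 |

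Psilocybin's rate is 40% in every row. Only the niacin rate changes.

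**Step 3: one data set, read two ways.** Suppose 6/15 on psilocybin have a psychological reaction and 6/15 on niacin have flushing.

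- Pooled: 6/15 − 6/15 = 0, so the rule is met.
- By type, psychological: 6/15 − 0/15 = 40 points. The Wilson limits are 0.198 to 0.643 for 6/15 and 0 to 0.204 for 0/15. The Newcombe lower limit is 0.40 − √(0.202² + 0.204²) = 0.11 and the upper limit is 0.40 + 0.243 = 0.64. Fisher's exact p = 0.017.

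**Step 4: a later visit.** If niacin's effects have gone and its rate is an assumed 10%, while psilocybin's is still 40%, P(met) = 0.08. The offset has largely disappeared.

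**The case against.** **Masking needs a niacin rate close to psilocybin's.** This stands. The documents give no niacin rate, so the size of the masking is conditional. A reader might infer that the rule can be met however large psilocybin's specific harm is. The table does not support that: with little niacin effect the rule is rarely met. Nor does a stronger sensory placebo always help. On the absolute-difference reading the chance falls from 0.42 to 0.035 as niacin goes from 40% to 80%, because the rule then fails on niacin's excess. Only the excess-only reading rises throughout.

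**The rule does respond to psychological harm.** This also stands, away from the ceiling. If both arms share a 50% rate of other events and psilocybin adds an independent 40% (both assumed), its rate is 1 − 0.5 × 0.6 = 70% against 50%, and P(met) falls from 0.42 to 0.24.

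**The rule applies at every visit and niacin's effects are transient.** This stands and limits the point to the dosing visit or a cumulative count. That is, however, when the reactions reported in up to 40% occur.

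**Niacin was not picked simply for its side effects.** Correct. Section 1.3.3.8 gives a different reason for preferring it to low-dose psilocybin: "because a partial response has been reported even with these low doses". Headache is listed for both agents, so it is not purely a niacin offset.

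**Harm by type remains visible elsewhere.** Grading (8.1.4), attribution (8.5), suicidality assessment at each randomized-phase visit (3.1) and dosing-day symptom ratings (6.2.3) are planned, and no stopping or efficacy decision depends on this endpoint. That lowers the stakes. It does not repair the endpoint, which uses none of these.

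**Conclusion.** The point holds in a limited form. As written, the pooled rule can be met at the dosing visit, or cumulatively, despite a large psilocybin-specific excess when niacin's event rate is near psilocybin's. With 15 per arm and psilocybin-specific events at 40%, the chance of meeting it is 0.005 with no niacin events and 0.42 with niacin at 40%. These figures rest on assumed niacin rates, no background events, participants as the unit and a 10-point absolute threshold.

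A reader might go further and conclude that the endpoint says nothing about safety or hides lasting harm. The documents do not support that: niacin's effects are described as transient, so later events are not offset in this way. The supported conclusion is that meeting the rule does not show the absence of a psilocybin-specific acute excess, and failing it may reflect niacin.

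**What to change.** In Section 2.3.2, drop the 10%-or-less criterion as a safety conclusion, define the rate as the proportion of participants with at least one event, and keep the pooled figure as descriptive only. Then:

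1. Compare the arms, with the difference and a 95% confidence interval, on the proportion with (a) psychological or psychiatric adverse events, including those on the dosing day, and (b) grade 2-3 adverse events as graded in Section 8.1.4. Show both separately for the dosing day and for the period after it.
2. Tabulate all physical dosing-day events by type and arm. Flag the niacin effects listed in Section 1.3.3.2 as expected, but do not remove them. Psilocybin's blood pressure, heart rate, nausea and headache events must stay in the comparison.

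The cost is protocol and SAP wording plus a category code on events already collected and graded, with no new visits or participants. The downside is wider intervals for smaller categories, and a visible psilocybin excess in place of a single pooled figure.

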2.3.3. Exploratory Endpoints

To test hypotheses concerning psychological therapeutic mechanisms, we will assess correlation and mediational influence of self-reported mystical states and psychological flexibility on changes in primary and secondary outcomes.

Exploratory endpoint A: Intensity of mystical experience (measured at the end of the medication dosing session), using the validated Mystical Experience Questionnaire. The hypothesis is that this will be a significant mediator of improvements in symptoms of depression and burnout.

[figure not shown]
Exploratory endpoint B: Psychological flexibility, using the AAQII, measured at 4 weeks after the medication dosing session. The hypothesis is that this will serve as a mediator of burnout.

Exploratory endpoint C: Interoceptive awareness, using the Multidimensional Assessment of Interoceptive Awareness.⁴⁸ The hypothesis is that this will be a mediator of improvements in symptoms of burnout.

3. Research Materials and Measures

3.1. Research Procedures

Participants will complete self-report and clinician-administered measures at baseline, prior to the medication dosing session, and at designated study visits (see figure next page).

Schedule for Activities during Randomized Phase									
Purpose	Screen	Prep	Prep	Medi- cation	Inte- gration	Inte- gration	Inte- gation	Follow -up	
Study day (approx)	-21-14	-7	-1	0	1	8	15	28	
Visit number		V1	V2	V3	V4	V5	V6	V7	
Research activity									
Demographics	X								
Eligibility Determination	X								
Medical exam	X								
Informed consent	X								
Caregiver contact info	X								
Blood draw	X								
Pregnancy screen (if applicable)	X			Х					
PI review of inclusion/exclusion	Х								

Page 18 Version 1.16, July 18, 2022

Informed Consent		X						
Mental health evaluation		Х						
Education re expectations	Х	Х						
Preparation psychotherapy		Х						
Urine screen	Χ							
Randomization				Х				
Medication (psilocybin or control)				Х				
Medication dosing monitoring				Х				
Integration psychotherapy					Х	Х	Х	
Adverse event reporting				Х	Х	Х	Х	
Un-blinding								X**
Measures								
Mont-Asberg Depression (MADRS)	Х	Х			Х	Х		Х
Beck Depression Scale		Х			X	Х		Х
Stanford Fulfillment Index		Х			X	Х		Х
Post-traumatic stress (PCL5)		Х			Х	Х		Х
Likelihood to leave job		Х			Х	Х		Х
Self-reported mystical exp				Х				
Moral injury symptom scale		Х						Х
Psychedelic Music Questionnaire					Х			
Psychological flexibility (AAQII)		Х				Х		Х
Interoceptive awareness (MAIA2)		Х			Х	Х		Х
Suicidality (C-SSRS)	Х	Х	Х	Х	Х	Х	Х	Х
Qualitative interview								Х
Adverse events, Suicidality	Х	Х	Χ	Х	X	Х	Х	Х

^{**}The unblinding will be done after the study coordinator has verified that the Day 28 measures have been completed.

Follow up measures for participants randomized to psilocybin							
Durance	Follow	Follow	Follow				
Purpose	-up	-up	-up				
Study day (approx.)	56	84	180				
Visit number	V8	V9	V10				
Measures							
Mont-Asberg Depression (MADRS)	Х	Х	Х				
Beck Depression Scale	Х	Х	Х				
Stanford Fulfillment Index	Χ	Х	Х				
Post-traumatic stress (PCL5)	Χ	Х	Х				
Likelihood to leave job	Χ	Х	Х				
Psychological flexibility (AAQII)	Χ	Х	X				
Interoceptive awareness (MAIA2)	Χ	Х	X				
Suicidality (C-SSRS)	Χ	X	X				
Qualitative interview							
Adverse events	Χ	Х	X				

